7.3.4 Safety analyses

Analysis of adverse events will be restricted to nintedanib-related serious adverse events, nintedanib-non-related serious adverse events and events of special interest.

Adverse events will be coded using the Medical Dictionary for Drug Regulatory Activities (MedDRA). Standard BI summary tables and listings will be produced. Adverse events with an onset between start of pulmonary rehabilitation treatment and end of trial will be assigned to the on-treatment period for evaluation. All randomized patients will be included in the safety analysis. In general, safety analyses will be descriptive in nature and will be based on BI standards. No hypothesis testing is planned.

Frequency, severity, and causal relationship of adverse events will be tabulated by system organ class and preferred term after coding according to the current version of the Medical Dictionary for Drug Regulatory Activities at the database lock.

Vital signs, physical examinations, or other safety-relevant data observed at screening, baseline, during the course of the trial and at the end-of-trial evaluation will be assessed with regard to possible changes compared to findings before start of pulmonary rehabilitation.

Analysis of laboratory data and electrocardiogram is not planned.

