4. TREATMENTS

4.1 INVESTIGATIONAL TREATMENTS

4.1.1 Identity of the investigational medicinal products

No study medication is included in this trial, this trial is a comparison of pulmonary rehabilitation versus standard care in patients with IPF already taking a stable dose of nintedanib. The active treatment arm will consist of a standard pulmonary rehabilitation regimen two or three times weekly for 12 weeks. Patients assigned to PR will be referred to a facility convenient for the patient. The pulmonary rehabilitation should follow the facility's standard regimen as long as the regimen meets basic standards (to be provided in the ISF). No study specific data collection is required by the PR facility, however standard treatment reports must be available to the investigator to document the attendance and progress of PR.

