4.2.1.2 Management of other adverse events

Adverse events related to the study procedures such as pulmonary rehabilitation, 6MWT [REDACTED] as well as unrelated adverse events, will be managed as clinically indicated. If a patient experiences an adverse event which impacts their ability to continue with pulmonary rehabilitation (if assigned) or ability to continue with the exercise testing, the clinical monitor should be consulted regarding continued participation in the trial prior to discontinuation.

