5.2.6.2 Adverse event and serious adverse event collection and reporting

The investigator shall maintain and keep detailed records of all AEs in their patient files.

Collection of AEs

The study design is of non-interventional nature regarding study medication and the study is conducted within the conditions of the approved marketing authorisation. Sufficient data from controlled interventional trials are available to support the evidence on the safety and efficacy of the studied BI drug. For this reason the following AE collection and reporting requirements have been defined.

The following must be collected by the investigator from signing the informed consent onwards until the end of the study:

- all Serious Adverse Events (SAEs) (regardless of causality),
- all Non-serious ADRs
- and AESIs

All SAEs, all non-serious ADRs, and AESIs including those persisting after study completion must be followed up until they are resolved, have been sufficiently characterized, or no further information can be obtained.

The investigator carefully assesses whether an AE constitutes an ADR using the information below.

Causal relationship of adverse event

The definition of an adverse reaction implies at least a reasonable possibility of a causal relationship between a suspected medicinal product and an adverse event. An adverse reaction, in contrast to an adverse event, is characterised by the fact that a causal relationship between a medicinal product and an occurrence is suspected.

Medical judgment should be used to determine the relationship, considering all relevant factors, including pattern of reaction, temporal relationship, de-challenge or re-challenge, confounding factors such as concomitant medication, concomitant diseases and relevant history.

Arguments that may suggest a **reasonable causal relationship** could be:

- The event is **consistent with the known pharmacology** of the drug
- The event is known to be caused by or **attributed to the drug class**.
- A **plausible time to onset of the event** relative to the time of drug exposure.

- Evidence that the **event is reproducible** when the drug is re-introduced
- **No medically sound alternative etiologies** that could explain the event (e.g. preexisting or concomitant diseases, or co-medications).
- The event is typically **drug-related and infrequent in the general population** not exposed to drugs (e.g. Stevens-Johnson syndrome).

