Distractions: During the exercise tests, access to the laboratory should be restricted to trial staff as much as possible. The noise level in the laboratory should be kept to a minimum, except for those sounds specifically related to the conduct of the test. This will ensure that the subject is able to concentrate on the task at hand, and will also ensure that the subject is attentive to the verbal encouragement provided by the designated member of the trial team.

Comfort with equipment: Subjects should be appropriately dressed for exercise (e.g., shorts or track pants, gym shoes, T-shirt or sweat shirt), and trial staff should ensure that the subject is comfortable with the equipment prior to starting the exercise.

Familiarity with test: Before starting exercise, a member of the trial team should make sure that the subject is completely familiar with the type of exercise that is to be performed, a practice test is expected prior to the baseline test at Visit 2 to allow patients to become familiar with the testing procedures.

Performance incentives: No external incentives for performance (i.e., rewards for performance) should be given to the subject, prior to or at any time during the exercise.

Personnel qualifications:

Exercise challenges should be conducted by adequately trained personnel with a basic knowledge of exercise physiology.

Technicians familiar with normal and abnormal responses during exercise and trained in CPR should be present throughout the tests.

Safety issues:

Cardiac (bradyarrhythmias, ventricular tachycardia, myocardial infarction, heart failure, hypotension, and shock) and non-cardiac (musculoskeletal trauma, severe fatigue, dizziness, fainting, body aches) complications of exercise challenges have been reported.

Consequently during the test, study personnel should be alert to any abnormal event. Indications to stop the test must be clearly established and known by the personnel involved in testing.

Symptoms such as:

- acute chest pain,
- sudden pallor,
- loss of co-ordination,
- mental confusion,
- extreme dyspnoea.

If the exercise test has been stopped for one of these reasons, the subject should be monitored in the laboratory until signs / symptoms / ECG modifications have completely cleared. Full CPR equipment should be available in the laboratory. Further participation in any exercise testing and continuation of the patient in the study should be discussed with the clinical monitor.

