7.8 SAFETY ANALYSIS

All safety analyses will be performed on the RS. The analysis will be performed as defined in the CTP. That is, analysis of adverse events will be restricted to nintedanib-related serious adverse events, nintedanib-non-related serious adverse events and events of special interest. Adverse events of special interest include DILI and GI Perforation.

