7.8.1 Adverse Events

The analyses of AEs will be descriptive in nature and will be based on BI standards (11). No hypothesis testing is planned. All analyses of AEs will be based on the number of subjects with AEs and NOT on the number of AEs.

For analysis, multiple AE occurrence data on the CRF will be collapsed into an AE event provided that all of the following applies:

- All AE attributes are identical (LLT, intensity, action taken, therapy required, seriousness, reason for seriousness, relationship [investigator defined drug-relatedness], outcome, AE of special interest)
- The occurrences were time-overlapping or time-adjacent (time-adjacency of 2 occurrences is given if the second occurrence started on the same day or on the day after the end of the first occurrence)

For further details on summarization of AE data, please refer to the guideline "Analysis and Presentation of Adverse Event Data from Clinical Trials" (11).

The analysis of adverse events will be based on the concept of treatment emergent adverse events. That means that all adverse events occurring between first nintedanib intake on/after randomization till 28 days after last nintedanib intake will be assigned to the treatment period. All adverse events occurring before first nintedanib intake will be assigned to 'screening' or 'post-randomisation' and all adverse events occurring after last nintedanib intake will be assigned to 'residual effect', 'post-treatment' or 'post-study' (for listings only). Also, all adverse events occurring between the start of an interruption and the end of interruption will be assigned to 'off-treatment' period in the listings. For details on the treatment definition, see Section 6.1.

According to ICH E3 (10), AEs classified as 'other significant' needs to be reported and will include those non-serious and non-significant AEs with (i) 'action taken = discontinuation' or 'action taken = reduced', or (ii) marked haematological and other lab abnormalities or lead to

significant concomitant therapy as identified by the Clinical Monitor/Investigator at a MQRM.

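### SAEs are classified only by their relation to nintedanib, so the planned tables cannot show which ones a rehabilitation session or a study exercise test caused

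*Protocol*

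**What the plan says.** Protocol 4.1.1 states the comparison: "No study medication is included in this trial, this trial is a comparison of pulmonary rehabilitation versus standard care". The randomised intervention is therefore rehabilitation, and nintedanib is background treatment in both arms.

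The safety plan is organised around the drug. Protocol 7.3.4 restricts the adverse event analysis to "nintedanib-related serious adverse events, nintedanib-non-related serious adverse events and events of special interest", and SAP 7.8 carries the same restriction forward. The events of special interest are hepatic injury (DILI in the SAP) and gastrointestinal perforation. Protocol 5.2.6.2 frames causality as a "causal relationship between a suspected medicinal product and an adverse event". Among the event attributes listed in SAP 7.8.1, the causal one is "relationship [investigator defined drug-relatedness", that is, relation to the drug.

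The protocol does recognise another kind of event. Section 4.2.1.2 deals with "Adverse events related to the study procedures such as pulmonary rehabilitation, 6MWT" and names them separately from unrelated events, but only to say how they are managed. Appendix 10.1.1 lists cardiac and non-cardiac problems and notes that such "complications of exercise challenges have been reported".

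**The concern.** The causal question asked of each SAE is about a treatment that both arms receive. It is not asked about the treatment that differs between arms, or about the exercise tests that the protocol itself imposes. A two-way split into nintedanib-related and not nintedanib-related puts a serious event provoked by exercise training in the same cell as, say, an unconnected fracture. A trial of an exercise programme in patients with progressive lung disease would then have no planned way to report how many SAEs investigators attributed to the programme or to its walk tests.

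**Working it through.** The point rests on text, and the plan gives no SAE rate to reproduce. I traced what would happen to an SAE caused by a session or a test, then asked whether the by-arm table fills the gap.

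**1. Path of the event through the plan**

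| Step | Place | Result for such an SAE |
|---|---|---|
| Collection | Protocol 5.2.6.2 | Collected, whatever the cause |
| Causality | Protocol 5.2.6.1 and 5.2.6.2 | Judged against a medicinal product only |
| Stored attribute | SAP 7.8.1 | Drug-relatedness |
| Analysis class | Protocol 7.3.4, SAP 7.8 | Not nintedanib-related |
| Special interest | Protocol 5.2.6.1, SAP 7.8 | No, unless hepatic injury or perforation |
| Tables | SAP 7.8.1 | Counted by arm, organ class and preferred term |
| Listings | Protocol 7.3 | Listed individually |

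Protocol 7.3.4 also promises a tabulation of causal relationship, but the only relationship defined anywhere is to the drug. No step adds a marker for a session or a test.

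**2. Does the by-arm SAE table substitute for rehabilitation harm?**

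Input from the documents: 145 patients per arm (Protocol 3.1). Assumptions: background SAE proportions of 5%, 10% and 20%, and an excess of 2 or 5 percentage points in the rehabilitation arm. Two points is 0.02 × 145 = 2.9 patients; five points is 0.05 × 145 = 7.25 patients.

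Precision comes from SE = √{[p₀(1−p₀) + p₁(1−p₁)]/145}. For 10% against 12%:

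- SE = √{(0.0900 + 0.1056)/145} = √0.001349 = 0.0367
- 95% half-width = 1.96 × 0.0367 = 0.072, about 7 points around a true difference of 2

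The same formula gives about ±5.5 points for 5% against 7%, and ±9.4 points for 20% against 22%.

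As a second view, this is the probability that a two-sided 5% pooled z-test of two proportions would reject. It is obtained by summing the binomial probabilities of all outcomes with |z| ≥ 1.96.

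| Background (assumed) | +2 points | +5 points |
|---|---|---|
| 5% | 10.5% | 35.7% |
| 10% | 8.4% | 25.2% |
| 20% | 7.1% | 17.7% |

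Protocol 7.3.4 plans no safety test, so these figures only illustrate how little a by-arm count says about a few extra events.

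**3. Does it substitute for walk-test harm?**

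Protocol 5.1.2.1 schedules four walk tests per patient: a practice test at Visit 1, then tests at Visits 2, 5 and 7. The practice test precedes randomisation, so an event in it has no arm to compare. The other three are scheduled in both arms. If they add the same risk r to a background b in each arm, the between-arm difference is (b + r) − (b + r) = 0, however large r is.

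**The case against.** The strongest reply is that nothing is lost. Every SAE is collected, reported within 24 hours, tabulated by arm and listed. Rehabilitation attendance goes into the eCRF (Protocol 6.2.2), and the reason for stopping a walk test early is recorded (Appendix 10.1.2). A reviewer could match SAE dates to sessions and tests. In a randomised trial the by-arm comparison is also the unbiased estimate of the intervention's harm, while an attribution made with knowledge of the arm is only a supplement. All of this stands, and it limits the point to the planned categories and tables. Hand matching is possible but not planned, and coincidence in time does not replace the investigator's judgement, which is already requested for the drug.

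A reader might infer three stronger things that the documents do not support:

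- *That such SAEs cannot be identified at all.* They remain visible by preferred term, arm and listing.
- *That no relation to a procedure is ever written down.* The fields of the AE form are not in the documents, so a narrative or alternative-cause field cannot be excluded.
- *That the regular safety review in Protocol 7.4 could not see a cluster.* That section does not say what the review examines. Section 4.2.1.2 and Appendix 10.1.1 also bring in the clinical monitor when an event affects rehabilitation or exercise testing, or when a test is stopped for listed symptoms.

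It is also fair to say that the SAE rates used above are assumed and the test is unplanned. The calculation does not show that unblinded attribution would detect an excess better. It shows only that the by-arm table leaves room for additional information.

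**Conclusion.** The point holds as a cheap improvement to the safety reporting. Both documents use the drug as the only causal axis, although "this trial is a comparison of pulmonary rehabilitation versus standard care" and the protocol foresees events from rehabilitation and walk tests. From the planned categories and tables, an SAE caused by a session or a study exercise test cannot be identified as procedure-related.

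The textual finding needs no assumption. The size does: at assumed background rates of 5% to 20% and the planned 145 per arm, the by-arm difference carries a 95% half-width of roughly 5 to 9 points when the true excess is 2 points. If fewer patients were randomised than planned, the interval is wider. The statement that the table is uninformative on walk-test harm assumes similar test attendance and similar risk per test in the two arms. The primary endpoint is unaffected.

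**What to change.** For each SAE, record the investigator's judgement on two items beside drug-relatedness: *related to a pulmonary rehabilitation session* and *related to a study exercise test*. In Protocol 7.3.4 and SAP 7.8, add one descriptive table or listing of SAEs by arm on these items. They need not be applied to the events of special interest, which were chosen for the drug.

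SAP section 4 records that the trial was terminated and that an abbreviated report is planned, so new form fields cannot help for events already collected. For those, assign the two items by medical review from the SAE reports, attendance dates and walk-test stopping reasons, and state in the report that this was done retrospectively.

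The cost is two items and one table, with no change to design, sample size or endpoints. The downside is small: attribution is made knowing the arm, and the rehabilitation item will be near zero in controls by construction. The table should therefore be labelled descriptive and read beside the by-arm SAE comparison, which remains the main evidence on harm.

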7.3.5 Pharmacokinetic and Pharmacodynamic analyses

There is no pharmacokinetic analyses planned for this trial.

7.4 INTERIM ANALYSES

No interim analysis is planned. A regular review of safety data will also be conducted to monitor the safety of patients in the trial.

7.5 HANDLING OF MISSING DATA

In efficacy analyses of continuous endpoints missing data will not be imputed. Multiple imputation will be used as a sensitivity analysis to handle missing data. Detailed description of multiple imputation will be included in the TSAP.

7.6 RANDOMISATION

Patients will be randomized in blocks to pulmonary rehabilitation groups with an equal probability of assignment to each treatment group (see [Sections 4.1.2](#), [4.1.3](#) and [4.1.4](#) for details). BI will arrange for the randomisation. The randomisation list will be generated using an Interactive Response Technology (IRT), which involves a pseudo-random number generator so that the resulting treatment will be both reproducible and non-predictable. Access to the codes will be controlled and documented. The block size will be documented in the clinical trial report.

7.7 DETERMINATION OF SAMPLE SIZE

In the 1199.187 6-month data, an unadjusted mean for absolute change from baseline in 6MWT distance of 4.9 meters (sd = 76.5) was observed for nintedanib. To conservatively estimate the sample size, a standard deviation of 85.0 is used in estimation. In the 2014 Cochrane Database of Systematic Reviews [[R18-1704](#)], a mean for absolute change from baseline in 6MWT distance of 44.3 meters was observed for pulmonary rehabilitation for interstitial lung disease. The minimal clinically important difference for the 6MWD for IPF patients with combined treatment of nintedanib and pulmonary rehabilitation versus IPF patients treated with nintedanib only is 30 meters [[R18-1767](#)].

In light of the available evidence, at least 254 patients would be required to provide 80% power to detect a difference in means of 30 meters between nintedanib and pulmonary rehabilitation combination treatment versus nintedanib by itself with a two-sided type-I error of 0.05. Assuming 10% drop out, at least 141 patients per arm, or 282 patients will be required. Calculations were performed using nQuery Advisor® 6.1 statistical package by Statistical Solutions Ltd. under the fixed term test of means with two groups option for student t-test with equal variance.

Difference in Means	Common Standard Deviation	Power (%)	Total N of randomized patients
30.0	77.0	80	210
30.0	85.0	80	254

8. INFORMED CONSENT, TRIAL RECORDS, DATA PROTECTION, PUBLICATION POLICY, AND ADMINISTRATIVE STRUCTURE

The trial will be carried out in compliance with the protocol, the ethical principles laid down in the Declaration of Helsinki, in accordance with the ICH Harmonized Tripartite Guideline for Good Clinical Practice (GCP), relevant BI Standard Operating Procedures (SOPs),

Standard medical care (prophylactic, diagnostic and therapeutic procedures) remains the responsibility of the treating physician of the patient.

The investigator will inform the sponsor immediately of any urgent safety measures taken to protect the trial patients against any immediate hazard, as well as of any serious breaches of the protocol or of ICH GCP.

The Boehringer Ingelheim transparency and publication policy can be found on the following web page: trials.boehringer-ingelheim.com. The rights of the investigator and of the sponsor with regard to publication of the results of this trial are described in the investigator contract. As a rule, no trial results should be published prior to finalization of the Clinical Trial Report.

8.1 TRIAL APPROVAL, PATIENT INFORMATION, INFORMED CONSENT

This trial will be initiated only after all required legal documentation has been reviewed and approved by the respective Institutional Review Board (IRB) / Independent Ethics Committee (IEC) and competent authority (CA) according to national and international regulations. The same applies for the implementation of changes introduced by amendments.

Prior to patient participation in the trial, written informed consent must be obtained from each patient (or the patient's legally accepted representative) according to ICH / GCP and to the regulatory and legal requirements of the participating country. Each signature must be personally dated by each signatory and the informed consent and any additional patient-information form retained by the investigator as part of the trial records. A signed copy of the informed consent and any additional patient information must be given to each patient or the patient's legally accepted representative."

The investigator must give a full explanation to trial patients based on the patient information form. A language understandable to the patient should be chosen, technical terms and expressions avoided, if possible.

The patient must be given sufficient time to consider participation in the trial. The investigator obtains written consent of the patient's own free will with the informed consent form after confirming that the patient understands the contents. Re-consenting may become necessary when new relevant information becomes available and should be conducted according to the sponsor's instructions.

The consent and re-consenting process should be properly documented in the source documentation.

8.2 DATA QUALITY ASSURANCE

A quality assurance audit/inspection of this trial may be conducted by the sponsor, sponsor's designees, or by IRB / IEC or by regulatory authorities. The quality assurance auditor will have access to all medical records, the investigator's trial-related files and correspondence, and the informed consent documentation of this clinical trial.

